3.13 Study Instrument

There are 2 study instruments used in this study; the baseline questionnaire and follow-up questionnaire which was described in 6.9.1.1 and saliva test was described in 6.10.

3.14 Data Collection

3.14.1 Baseline

The facilitators from the Kota Belud Dental Clinic staff will be trained and standardised for the conduct of this study. A training manual will be given to each facilitators. They will be briefed and their understanding on every item of the questionnaire and worksheets will be scrutinised and refined as intended by the study. Any difficult words identified by the facilitators will be changed to a simpler alternative. Translated words into Bajau dialect will be discussed and decided upon for standardisation.

From face-to-face interviews with the participants, information regarding demographics details and baseline information about BQ chewing behaviour, BQ composition, BQ dependency levels, reasons for chewing and readiness and self-perceived barriers to quit will be garnered. Face-to-face interview mode was chosen as a method to complete the questionnaire to obtain a better response rate and to minimise inaccurate response due to illiteracy issues and participant's poor comprehension due to age.

Participant's baseline saliva samples will be gained for biomarker comparison as a method to verify the intervention's self-reported effectiveness. Saliva samples collected will be transported within 2-3 hours to the lab facilities to be stored under -80 °C temperature. The transportation of these saliva samples will be monitored and carried out by the main researcher.

3.14.2 Follow up at 22-day (short term)

Information regarding participant's personal particular, participant's compliance, current chewing status, number of cut-down of habit by the participants (quid/day), total number of session attended and reasons if absent and the BQ composition if participants are still chewing will be gained through a face-to-face interview with a follow-up questionnaire.

Participant's 22-day saliva samples will be gained to evaluate the short term effectiveness of the intervention and to verify the self-reported outcomes. The levels of areca nut and cotinine biomarkers in saliva samples (via liquid chromatography mass spectrometry) will be evaluated. The cut-off levels for areca nut biomarkers are arecoline (60 ng/mL), arecaidine (10 ng/mL), guvacoline (20 ng/mL), and guvacine (6 ng/mL) and the cut-off levels for cotinine levels (10 ng/mL). Biomarkers level above this cut-off points represent that participants have still not ceased the habit.

3.14.3 Follow up at 1-month and 3-month

Information regarding participant's personal particulars, participant's current chewing status, number of cut-down of habit by the participants (quid/day) and the BQ composition if participants are still chewing will be taken through face-to-face interview with a follow-up questionnaire.

At 3-month, participants' saliva samples will be collected to evaluate the intermediate term effectiveness of the intervention and to verify the self-reported outcomes. The same cut-off levels of AN and cotinine will be used to represent the participant's cessation of their chewing habit.

3.15 Data Management and Analysis

3.15.1 Study variables and operational definition

The baseline questionnaire used in this study contains 6 parts and their variables are as described in the following tables:

Part A – Demographics

Conceptual Definition	Operational Definition	Type of Variable	Scale of Measurement
Age	Participant's age as of last birthday	Continuous/ Numerical	Years
Gender	Participant's gender	Categorical	1- Male 2- Female
Ethnic	Participant's ethnic background	Categorical	1- Bajau 2- Dusun 3- Irranun 4- Malay 5- Chinese 6- Indian 7- Others (specify)
Marital Status	Participant's current marital status	Continuous	1- Single 2- Married 3- Widowed/ Divorcee
Education Level	Participant's highest level of education	Categorical	1- University and above 2- Diploma 3- Certificate 4- STPM/ Matriculation 5- SPM 6- PMR 7- Primary school 8- No formal education
Occupation	Participant's occupation	Continuous	1- House maid 2- Unpaid worker or home maker 3- Self employed 4- Private employee

5- Government or semi government employee

Monthly Income	Participant's monthly individual income	Continuous	1 < RM 500 2 RM 501 – RM 999 3 RM 1000 – RM 2999 4 RM 3000 - RM 4999 5 RM 5000 and above
----------------	---	------------	--

Part B – BQ Chewing Behaviour & Other Concomittant Risk Habits (Maling TH, 2016 & Tahir Z et al., 2003)

Conceptual Definition	Operational Definition	Type of Variable	Scale of Measurement
Current Chewing Status	Did the participant chewed at least 1 BQ for the past 1 week	Categorical	0- No such habit 1- Habit currently practised 2- Past habit and now has stopped
Age started chewing	What was the age the participant started chewing BQ	Continuous/ Numerical	
Years have ceased the habit (for ex-chewers)	How long the ex-chewer has ceased the BQ habit	Categorical	1- A month ago 2- 3 months ago 3- About a year ago 4- Already more than 5 years
Frequency of chewing BQ	How often current BQ chewers chewed BQ	Categorical	1- Daily 2- Two-three times a week 3- Few times a month 4- I am an occasional betel quid chewer 5- Others, please specify
Number of BQ chewed per day	Number of BQ chewed by the participants in a day	Continuous/ Numerical	
Special practice (relevant to Kota Belud)	Do participants keep their BQ in their mouths overnight	Categorical	1- Yes 2- No

Past quit attempts	If the participants have attempted quitting chewing before in their life	Categorical	1- Yes 2- No
Number of past quit attempts	The number of attempts participants have tried to cease the behaviour in the entire lifetime	Continuous/ Numerical	
Current Smoking Status	Did the participant smoke at least 1 cigarette for the past 1 week	Categorical	0- No such habit 1- Habit currently practised 2- Past habit and now has stopped
Frequency of smoking	How often does the current smoker smokes	Categorical	1- Daily 2- Two-three times a week 3- Few times a month 4- I am an occasional smoker 5- Others, please specify
Current Drinking Status	Did the participant drink at least 1 pint of alcohol for the past 1 week	Categorical	0- No such habit 1- Habit currently practised 2- Past habit and now has stopped
Frequency of alcohol drinking	How often does the current alcohol drinker drinks	Categorical	1- Daily 2- Two-three times a week 3- Few times a month 4- I am an occasional drinker 5- Others, please specify
Medical problems	Medical conditions of the participant	Categorical	1- Yes (specify) 2- No

Part C – BQ Composition (Tahir Z & Doss JG, 2003)

Conceptual Definition	Operational Definition	Type of Variable	Scale of Measurement
Betel quid composition	The composition of BQ chewed by participants	Categorical	a. Areca nut b. Tobacco c. Betel leaf d. Lime e. Gambir f. Others (please specify)

Part D – Reasons for betel-quid chewing scale (RBCS) (Little MA et al., 2014)

Conceptual Definition	Operational Definition	Type of Variable	Scale of Measurement
Construct 1: Reinforcement			
1. I like the taste	Participants chews BQ because they enjoy the quid's taste	Categorical	0 = No 1 = Yes
2. I like to have something in my mouth at all times	Participants chews BQ because they are fond of having something in the mouth at all time period	Categorical	0 = No 1 = Yes
Construct 2: Social/cultural			
3. All of my friends chew	Participants chews BQ because all of their friend circle chews it as well	Categorical	0 = No 1 = Yes
4. My family members chew	Participants have family members who chews BQ (children, brothers, sisters, parents, grandparents, aunts, uncles, and other family members)	Categorical	0 = No 1 = Yes

5. It's rude not to chew	Participants chews BQ because it was considered rude or an insult if they didn't	Categorical	0 = No 1 = Yes
--------------------------	--	-------------	-------------------

6. People will not respect me if I don't chew	Participants chews BQ for respect from surrounding social circle	Categorical	0 = No 1 = Yes
---	--	-------------	-------------------

Construct 3: Stimulation

7. It relaxes me	Participants feels relax as they chew BQ	Categorical	0 = No 1 = Yes
------------------	--	-------------	-------------------

8. It gives me energy	Participants claims chewing BQ gives them energy	Categorical	0 = No 1 = Yes
-----------------------	--	-------------	-------------------

9. It helps me make decisions	Participants feels chewing BQ helps them to make decisions	Categorical	0 = No 1 = Yes
-------------------------------	--	-------------	-------------------

10. I like the way it makes me feel	Participants claims likes the feeling of chewing a BQ	Categorical	0 = No 1 = Yes
-------------------------------------	---	-------------	-------------------

Others

11. Insult if do not chew BQ in social situations	Participants will be considered insulting a social situation if he or she didn't chew	Categorical	0- Never 1- Seldom 2- About Half the Time 3- Usually 4- Almost always
---	---	-------------	---

12. Importance of chewing betel quid was in the social situations	Participants feels it's important to chew BQ during following functions (birthdays, fiestas, anniversaries (of deaths), parties, rosaries, and working)	Categorical	0 = Not important 1 = Slightly Important 2 = Moderately Important 3 = Important 4 = Extremely important
---	---	-------------	---

Part E – Betel Quid Dependency Scale (T.A. Herzog et al., 2014)

Conceptual Definition	Operational Definition	Type of Variable	Scale of Measurement
Domain 1: Physical and psychological urgent need			
1. Can't go on without betel nut/quid	Participant have urgent need to chew BQ	Categorical	0-No 1-Yes
2. Difficulty concentrating after reducing use	Participants have difficulty in concentration after reducing BQ chews in a day	Categorical	0-No 1-Yes
3. Experienced depression or drowsiness	Participant experiencing depression or drowsiness as craving or withdrawal symptoms	Categorical	0-No 1-Yes
4. Strong craving after reducing/stopping to chew	Participant experiencing strong craving after reducing number of chews or ceasing the habit	Categorical	0-No 1-Yes
5. Spend time to find when not available	Participants spend a considerable amount of time to search for BQ if it's not available	Categorical	0-No 1-Yes
6. Travel great distance to find when not available	Participants travel a considerable amount of distance to search for BQ if it's not available	Categorical	0-No 1-Yes
7. Felt agitated, irritated, or anxious after reducing	Participant feels agitated, irritated, or anxious after reducing chews per day	Categorical	0-No 1-Yes

Factor 2: Increasing dose			
8. Trouble stopping once started chewing	Participant face difficulty to stop chewing once started the habit	Categorical	0-No 1-Yes
9. Ever chewed non-stop	Participant's past experience whether he or she has chewed BQ non-stop in a day	Categorical	0-No 1-Yes
10. Increased the amount of use after first use	Participants' past experience whether they increased the amount of BQ ingredients or the number of chews after first use	Categorical	0-No 1-Yes
11. Felt the need to increase amount of use periodically	Whether participants have ever felt the need to increase the number of chews or amount of BQ ingredients periodically	Categorical	0-No 1-Yes
12. Often chewed betel nut/quid more than expected	Participant's experience whether he or she often chewed BQ more than expected or routinely practiced	Categorical	0-No 1-Yes
Factor 3: Maladaptive use			
13. Continue chewing after teeth loose nor wiggle	Participant's experience of continuing chewing BQ even when teeth were loose	Categorical	0-No 1-Yes
14. Continue chewing if you had sensitive teeth	Participant's experience of continuing chewing BQ even when they had sensitive teeth	Categorical	0-No 1-Yes
15. Continue chewing if experienced mouth ulcers	Participant's experience of continuing chewing BQ even when they had mouth ulcers	Categorical	0-No 1-Yes
16. Reduced or given up activities because of chewing	Participant's experience of reducing or giving up other activities to chew BQ	Categorical	0-No 1-Yes

Part F – Readiness & Self-Perceived Barriers To Quit Habit (Brown RA, 2003)

Conceptual Definition	Operational Definition	Type of Variable	Scale of Measurement
1. Readiness to quit chewing habit	Participant's readiness to quit behaviour	Categorical	0- Will continue and accept the consequences 1- Attempted to quit but does not think it will succeed 2- Will reduce or modify habit 3- Have great determination to quit and thinks will succeed
2. Self -perceived barriers in quitting chewing habit	Participant's self-thought barriers or difficulties in quitting chewing behaviour	Categorical	1- Without BQ, I will be anxious 2- Without BQ, I will feel down, sad and depressed 3- Without BQ, I will feel easily irritable 4- Without BQ, I will gain weight 5- Without BQ, I will not be respected in my community/family 6- Without BQ, I will lose my social circle 7- It's hard to quit, I have tried in the past 8- I have thoughts to quit but I don't know how to quit 9- I don't think it is important to quit 10- Other, please specify:

3.15.2 Data Entry

All data collected will be entered into a Microsoft Excel database, cleaned and then exported to Statistical Package for Social Sciences (SPSS) version 29.0. Descriptive analysis through means and standard deviation will be reported for continuous variable and in the form of percentage for categorical variables and individual items in each domain. A mean and standard deviation also will be calculated for the aggregated domain score. Data of participants that attended all sessions will be analyzed for the cessation rate measurements.

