3.0 MATERIALS AND METHOD

3.1 Overview of the Study design

This is a comparative prospective community trial which utilises a cluster randomised controlled trial design involving a Bajau indigenous community in Sabah, Malaysia with a 1:1 allocation ratio. The clusters are Bajau villages that practises BQ chewing habits in Kota Belud district in Sabah. The Bajau villages are the unit of randomisation. There are 39 Bajau villages in Kota Belud, Sabah (Tahir Z et al., 2003).

The clustered randomised controlled trial study design was selected as there was a high tendency of crossover if both intervention and control groups are randomised within the same village. Individuals allocated to a control group may inadvertently receive some aspects of the intervention if they are in proximity to the individuals in intervention group (Hahn S et al (2005). Thus, clustered randomised trial is the best available design for researchers who evaluating intervention that operates at group level, that manipulates the social and physical environment and cannot be delivered to individual participants without any substantial risk of contamination (NIH, 2022).

The eligible villages will be randomised into intervention and control groups based on the required sample size. The intervention group will receive an educational booklet and a structured BQ cessation program which will be cross- culturally adapted first based on a clinical trial (BENIT) by Paulino YC et al. (2020) for a Malaysian high risk population. The control group will only receive an educational booklet.

Baseline information on participant's demographics, BQ chewing behaviours, BQ composition, BQ dependency levels, reasons for chewing, the readiness and self perceived barriers to cease habit will be obtained prior to the commencement of the intervention. The

same participants will be followed-up at 22-day and 3-month after commencement of intervention to assess their of quitting experience and impact of the intervention. Day 22 follow-up was kept in this study as it will enable study results to be compared with similar BQ cessation studies in other parts of the world such as in Pacific Islands (Moss J. et al., 2015 and Paulino YC et al., 2020).

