3.4 Sample Size

The sample size needed for this study will be calculated from a previous study performed by Herzog TA et al. (2022). The sample size was calculated using OpenEpi Version 3 software with the following assumptions:

 Margin of error (α error)	:	0.05
 Power of study ($1-\beta$)	:	0.8
 Allocation Ratio	:	1
 Percent of Exposed with Outcome	:	38.64 %
 Percent of Unexposed with Outcome	:	9.09 %

A total of 76 participants are needed for this study and 38 participants in each arm. After calculation of 20% dropout at 22th day and in 3 months (16 people), a revised total of 92 participants are needed for this study with 46 participants in each arm (Figure 3.1)

[figure not shown]

[figure not shown]
Figure 3.1 Flow of the Participant Allocation in the Study

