3.8 Selection criteria

The **inclusion criteria** for this study is as follows:

- ✚ A self-reported BQ chewer who has been chewing BQ for the past 6 months with atleast 2-3 chewing episode per week. The ingredient of BQ must include AN without or without smokeless tobacco.
- ✚ Other optional ingredients such as slaked lime and betel leaf are allowed.
- ✚ Age of participant must be 18 year old or above
- ✚ Participants must be residing in study location (Kota Belud, Sabah)
- ✚ Ability to comprehend, converse and read in Bahasa Melayu and their local language (Bajau)
- ✚ Participants who are able to provide written consent and agree to comply with all protocol-specified procedures such as providing saliva samples, participating in five 1-2 hours sessions of intervention over 22 days and agree to attend follow-up sessions on first and third month

The **exclusion criteria** for this study are as below:

- ✚ Non-Malaysian citizen
- ✚ Participants who are not willing to quit the BQ chewing habit at the time of the study
- ✚ Women who are pregnant or nursing at the time of study
- ✚ Individuals with psychiatric illness or special social situations that would limit their compliance with study requirements

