3.9 Participant/Subject Withdrawal Criteria

The Main Researcher may withdraw (remove) a participant from some study components at her discretion if participant is non-compliant with required study regimens or procedures.

A participant can voluntarily withdraw from participation in some or all components of a study for which he or she has previously consented if he or she has a valid reason. Withdrawn participants will be replaced only if required sample size is not fulfilled.

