3.10.3.2 Implementation of the Study

Control Group

The community screening program for the control group will be organised at the community hall. Villagers who attended the screening program will first be registered and screened for eligibility to participate in the study (**Checkpoint 1**). The eligible participants will be briefed on the nature of the intervention and will be invited to participate. A copy of 'Patient Information Sheet' (PIS) (Appendix A) will be explained and given for reference about the study details and written informed consents (Appendix B) will be obtained from the villagers prior admitting them into the study.

Only consented participants will be interviewed by the trained interviewers (**Checkpoint 2**). Information regarding demographics details and baseline information of BQ chewing behaviours, BQ composition, BQ dependency levels, reasons for chewing, readiness and self-perceived barriers to quit will be obtained. No intra-oral clinical examination will be carried out in this study.

Upon completing of the interview, participants will be given an educational booklet which contains general information regarding AN and BQ, risk associated with BQ chewing behaviour, cessation strategies that are modeled after tobacco cessation and researcher's contact information. After an one-to one explanation about the educational booklet to the participants by the interviewer, they will be ushered to saliva collection counter (**Checkpoint 3**) to provide their baseline saliva sample. Participants will be thanked and given a token of appreciation before they are ushered out of the community hall.

Participants will be provided with an appointment card to return on the 22-day, 1-month and 3-month for follow-up. Follow-up questionnaire and saliva samples will be taken on 22-day and 3-month, whereas a community perception analysis will be performed at 1-

month together with completion of follow-up questionnaire. The summary of participant's flow for the control group is illustrated in Figure 3.6.

[figure not shown]

Figure 3.6 Summary of Participant's Flow for the Control Group in this study

Intervention group

Screening (Day 0)

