The community screening program for the intervention group will be organised at the community hall on a Saturday. Villagers who attend the screening program will first be registered and screened for eligibility to participate in the study (**Checkpoint 1**). The eligible participants will be briefed on the nature of the intervention and will be invited to participate. A copy of 'Patient Information Sheet' (PIS) (Appendix A) will be given for the reference about the study details and written informed consents (Appendix B) will be obtained from the villagers prior admitting them into the study.

Only consented participants will be interviewed by the trained interviewers (**Checkpoint 2**). Face-to-face interviews will be carried out to gain participant's information regarding demographics details and baseline information of BQ chewing behaviours, BQ composition, BQ dependency levels, reasons for chewing, readiness and self-perceived barriers to quit habit. No intra-oral clinical examination will be carried out in this study.

Upon completion of the interview, participants will be briefly explained and given an educational booklet which contains general information regarding AN and BQ, risk associated with BQ chewing behaviour, cessation strategies that are modeled after tobacco cessation and researcher's contact information. They will then be ushered to saliva collection counter (**Checkpoint 3**) to provide their baseline saliva sample.

Participants will be thanked and given a token of appreciation before being ushered out of the community hall and will be reminded to return the next day (Sunday) to initiate the first support session for the cessation intervention. For every intervention session attended by the participants, they will be monetarily incentivized for their time and commitment for cessation. Appointment card will be provided to ease participants reference of support session dates.

A self explanatory video presentation regarding general information of AN and BQ, the ill health effects of BQ and introduction and importance of cessation program will be continuously played **for the non- chewers in the village hall** to increase their knowledge and awareness while they are waiting for their family members. who are undergoing the screening. This can help maximise their support for their loved ones who are trying to quit the risk habit.

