3.12 Outcome of the Study

3.12.1 Primary Outcome Measures

Change in the number of participants who self-reported that they had quit BQ chewing will be measured through follow-up questionnaire at day 22. This will represent the short-term cessation prevalence achieved by the study.

Change in the number of participants who self-reported that they had quit BQ chewing will be measured through follow-up questionnaire at Month-3. This will represent the intermediate-term cessation prevalence (stay-quit) achieved by the study.

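### The cessation rate is to be computed on participants who attended all sessions, a post-allocation filter that falls unequally on the two arms

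*Protocol*

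**What the plan says.** Section 3.15.2 of the protocol ends its short analysis paragraph with "Data of participants that attended all sessions will be analyzed for the cessation rate measurements". Nothing else in the protocol says who enters the cessation analysis.

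Cessation is the main question of the trial. Section 1.7 sets the hypothesis as a difference in cessation rate between the arms at 3 months. Section 3.12.1 makes self-reported quitting the primary outcome at Day 22 and again at Month 3: "Change in the number of participants who self-reported that they had quit BQ chewing will be measured through follow-up questionnaire at Month-3".

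The arms have different schedules. The intervention arm has support sessions on Days 1, 8, 15, 18 and 22 (section 3.10.3.2 and Table 3.4). For the other arm, section 3.1 says "The control group will only receive an educational booklet", and section 3.10.3.2 adds "Participants will be provided with an appointment card to return on the 22-day, 1-month and 3-month for follow-up".

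The word session is also used for follow-up visits. The inclusion criteria in section 3.8 require agreement to "participating in five 1-2 hours sessions of intervention over 22 days and agree to attend follow-up sessions on first and third month".

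**The concern.** Attending every session happens after allocation and can depend on how quitting is going. Quit day is Day 15, and two further sessions follow on Days 18 and 22. Someone in an intervention village who fails to quit and stays away on Day 18 drops out of the denominator. A control who fails to quit has no Day 18 session to miss. If people who miss sessions quit less often than those who attend, the filter raises the intervention cessation rate without any effect of the programme.

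At stake is the validity of the primary comparison, because a difference could appear when the programme adds nothing to the booklet. The filter also removes people from one arm beyond the dropout for which section 3.4 allows.

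**Working it through.** **The plan's own sample size.** Inputs from section 3.4: 38.64% against 9.09%, α = 0.05, power 0.80, ratio 1. A two-sided comparison of two proportions with continuity correction gives 38 per arm, which matches. Enrolment of 92 reproduces as 76 × 1.2 = 91.2, rounded up to 46 per arm.

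**Which visits the filter covers.**

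| Reading of sessions | Intervention must attend | Control must attend |
|---|---|---|
| Support sessions only | Days 1, 8, 15, 18, 22 | none |
| Follow-up visits also count | Days 1, 8, 15, 18, plus Day 22, 1 month, 3 months | Day 22, 1 month, 3 months |

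The filter is unequal on both readings: five extra conditions on the first, four on the second.

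**Bias with no true effect.** The protocol gives no attendance rates, so the values of *a* and *f* below are assumptions. Let *p* = 0.0909 be the quit rate in both arms, *a* the share attending everything, and *f* the quit rate of non-attenders relative to *p*. Since *a* × (rate in attenders) + (1 − *a*) × *f* × *p* = *p*, the rate in attenders is *p* × [1 − (1 − *a*) × *f*] / *a*. For example, with *a* = 0.6 and *f* = 0 it is 0.0909 / 0.6 = 15.15%, which is 6.06 points above 9.09%.

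First reading, false advantage in percentage points:

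| *f* | *a* = 0.8 | *a* = 0.6 | *a* = 0.5 |
|---|---|---|---|
| 0 (non-attenders never quit) | 2.3 | 6.1 | 9.1 |
| 0.5 (half the overall rate) | 1.1 | 3.0 | 4.5 |
| 1 (unrelated) | 0 | 0 | 0 |
| 1.5 (non-attenders quit more) | −1.1 | −3.0 | −4.5 |

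Second reading, with 80% of both arms attending all follow-ups and the intervention arm also attending four extra sessions at rate *s* each, independently:

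- *s* = 0.90: *a* = 0.8 × 0.9⁴ = 0.525. At *f* = 0, 17.32% against 11.36%, or 6.0 points; at *f* = 0.5, 13.20% against 10.23%, or 3.0 points.
- *s* = 0.95: *a* = 0.8 × 0.95⁴ = 0.652. At *f* = 0, 13.95% against 11.36%, or 2.6 points; at *f* = 0.5, 11.52% against 10.23%, or 1.3 points.

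**False-positive rate.** This was simulated under the null: 200,000 runs, 46 per arm, an individual-level two-sided z-test at 0.05 and no clustering. Controls returned at 80% regardless of quitting, and the true quit rate was 9.09% or 20%.

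| Full attendance: quitters / non-quitters | Type I error at 9.09% | Type I error at 20% |
|---|---|---|
| 0.8 / 0.8 | 0.048 | 0.051 |
| 0.9 / 0.7 | 0.061 | 0.073 |
| 0.9 / 0.5 | 0.124 | 0.177 |
| 0.8 / 0.4 | 0.151 | 0.218 |

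In the last three rows most of the error favours the intervention, and in the last two nearly all of it does.

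**Numbers left in the intervention arm.**

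- 90% independent attendance per session: 46 × 0.9⁵ = 27.2 over five sessions; 46 × 0.9⁴ = 30.2 over the four extra sessions, before follow-up losses.
- 95%: 46 × 0.95⁵ = 35.6, or 46 × 0.95⁴ = 37.5.
- If the same people miss every session, 90% attendance leaves 46 × 0.9 = 41.4.
- Keeping 38 of 46 needs 38/46 = 82.6% full attendance. That is 0.826^(1/5) = 96.3% per session over five independent sessions, or 0.826^(1/4) = 95.3% over four.

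**The case against.** **Other analyses are not excluded.** The sentence does not say that full attenders are the only set, and a statistical analysis plan that is not at hand might add an analysis of everyone. That is possible. But the protocol fixes this rule without qualification and names no other, so it has to be judged as written.

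**The word is less ambiguous than it looks.** The follow-up questionnaire records intervention sessions attended, and section 3.10.1.1 speaks of group sessions, so usage leans to the first reading. Section 3.1 does not list the 1-month visit, and the intervention-arm description passes from Day 22 to Day 90. This stands, and it makes the second-reading figures the less likely ones. The first reading is also the one on which controls face no filter at all.

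**The first-reading figures assume no loss among controls.** If 80% of controls return and the same *f* applies to them, and the intervention shares already include follow-up loss, the excess at *a* = 0.8 / 0.6 / 0.5 falls to 0.0 / 3.8 / 6.8 points at *f* = 0 and 0.0 / 1.9 / 3.4 at *f* = 0.5. This stands as a limit on size.

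**The direction is not proven.** Some people may stop coming because they have already quit, and then the sign reverses, as the *f* = 1.5 row shows. Payment also works against absence: "For every intervention session attended by the participants, they will be monetarily incentivized for their time and commitment for cessation". Relapsers are encouraged to try again. Bias towards the programme is therefore an inference, though a plausible one.

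**The loss of numbers is not decisive.** At the plan's rates, with continuity correction and ignoring clustering, 36 against 46 gives power of about 0.84, 30 against 46 about 0.80 and 27 against 46 about 0.77. Recruitment takes all eligible villagers and adds village pairs until the target is met (sections 3.5 and 3.6). The shortfall is secondary to the bias.

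None of these points makes the filter equal between the arms.

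**Conclusion.** The concern holds. The protocol's only rule for the cessation analysis selects participants on attendance after allocation, and the selection is heavier in the intervention arm on either reading. That conclusion rests on the text alone.

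The size and direction of the bias rest on assumptions, because no attendance data are given. With 9.09% quitting in both arms, non-attenders quitting at between zero and half the overall rate, and 50% to 80% full attendance, the false advantage on the first reading runs from 1.1 to 9.1 points. Comparable selection among controls lowers this to between 0.0 and 6.8. It is zero if attendance is unrelated to quitting and negative if non-attenders quit more often. Because the rule governs the primary outcome and can produce a difference where none exists, it must be corrected before the analysis.

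**What to change.** Replace the sentence in section 3.15.2 with: *All consented participants are analysed in the arm to which their village was allocated, regardless of the number of sessions attended.* Keep full attenders as a supportive analysis only, and define there which visits count as sessions.

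Two additions are useful but secondary, and a statistical analysis plan could carry them:

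- One rule for missing chewing status, the same in both arms, with a sensitivity analysis such as counting missing as still chewing. Losses may differ by arm: payment per session is described for the intervention arm, while the control section mentions only a baseline token and does not say whether controls are paid at follow-up.
- In section 3.9, where the main researcher "may withdraw (remove) a participant from some study components at her discretion", a statement that such participants stay in follow-up and in the denominator, and that replacing them does not remove them from the analysis.

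The cost is wording. Chewing status is already scheduled in both arms, so no new data are needed. The reported intervention rate will probably be somewhat lower than among full attenders. At the plan's rates, ignoring clustering as section 3.4 does, 46 against 46 with nothing missing has power of 0.93 without continuity correction (0.88 with it). If 20% in each arm are missing and counted as chewing, the rates become 0.8 × 38.64% = 30.9% and 0.8 × 9.09% = 7.3%, and power is 0.83 without the correction or 0.76 with it. Since the plan's 38 per arm uses the correction, the sample size should be checked again if that rule is made primary.
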